8.5 Preparation and labelling of Investigational Medicinal Product and Placebo

Anti-ST2 and the placebo will be provided by Genentech to the Pharmacy in packaged vials with unblinded outer labels. Both the IMP and placebo will be ready for use and will not need to be diluted prior to administration. Allocation of trial medication (Anti-ST2 or placebo) will be managed by Sealed Envelope (web based randomisation system). The Anti-ST2 and placebo will be prepared and a blinded yellow label applied to the syringe by unblinded trial personnel (see section 7.3-7.5 on Blinding and Randomisation). All information will be documented on an unblinded participant accountability log and the enrolment log by the unblinded trial personnel, the pharmacist will maintain their own unblinded accountability logs.

8.6 Dosage schedules

See figure 1 for dosing schedule. In animal trial and phase I human studies both, intravenous and subcutaneous (SC) routes were used, with no significant difference in safety. For ease of administration we will be using the SC route in this trial. The drug dose is fixed at 490mg every 4 weeks for 12 visits.

A window of up to 4 weeks will be allowed within which a participant will be able to delay or miss taking a scheduled dose. A delay will then be carried through to all their subsequent study visits. If the participant misses a dose it will be recorded in the notes and the next scheduled dose will be administered. Participants will be allowed to miss a single dose of the study drug (See Section 7.7) and are permitted up to a 4 week treatment delay.

8.7 Dosage modifications

There will not be any dose modification during the trial (see Section 8.10 for non IMP medication changes).

If a participant has an anaphylactic reaction to the drug or placebo, they will discontinue from protocolled treatment but remain in follow-up. If the drug was stopped due to a clinical reason such as allergic reaction, we will err on side of caution and not restart the drug in the same participant.

No information on overdose, maximum-tolerated dose, or dose-limiting toxicities has been established at this time.

8.8 Known drug reactions and interaction with other therapies

There are no known drug reactions and interactions with other therapies. See Section 13.6.1 Possible Side Effects of the Trial Medication and the Placebo.

8.9 Concomitant medication

There are no restrictions on concomitant use of other medications.

8.10 Trial restrictions

There is no scope in this study for dose reduction of the IMP, however participants are permitted to miss a single dose. The dose for the patients' standard of care therapy(s) for COPD will be maintained where possible, however this will be left up to the clinician's discretion. The clinician will also have discretion to alter any concomitant medication(s) that are unrelated to their COPD as required.

Participants are required to complete the scheduled clinic visits within the time windows allowed in the protocol. As the administration of trial medication is only at the clinic, and the need to maintain the required intervals between dosing, it is very important to adhere to the time windows for each visit.

All study visits have been given a window of +/- 7days to allow for flexibility, apart from visit 14 which will have a window of +/- 14 days. Any visits completed outside of this window will be logged as protocol deviations. Participants will be permitted where required, up to a 4 week treatment delay of a scheduled dosing visit, to allow for adverse events, holidays or other unexpected events. The participant can miss a dose and receive their next dose at the scheduled visit, or they can receive a delayed dose when available and their subsequent visit schedule would be altered accordingly to incorporate the delay (see Section 8.6). Depending on the nature of the AE/SAE it will be left to the clinician's discretion to determine if the patient should be withdrawn from the study. Participants that are delayed more than 4 weeks (more than a single dose) will be withdrawn.

Persistent deviations would indicate potential non-compliance and will have to be discussed with the Chief Investigator and the Sponsor regarding possible withdrawal. Those participants who are planning to take more than a 4 week consecutive holiday would not be included in the study, this will be asked at screening.

Participants should be compliant in taking their daily COPD medications during the course of the trial. Dose and regimen of routine medications should not be changed during the course of the trial (screening, treatment, and follow-up periods) except for treatment of an exacerbation or unless absolutely medically necessary. Baseline treatment should be maintained at the same dose and regimen at it was at the time of entry to the trial.

If changes are absolutely necessary for reasons other than to treat the participant for COPD exacerbation, this should be discussed with the Local Clinical Monitor, and documented in the participant source data including the medical rationale for the change from the treating physician. The follow-up period is also an important part of the study to assess therapeutic efficacy and changes following the last dose of anti-ST2 should be avoided. After the participant completes the final clinic visit at week-48, investigator may adjust the dose or change the COPD medications without consequence to the trial objectives.

8.11 Assessment of compliance with treatment

All doses of the trial treatment will be administered SC at the investigational site by blinded research staff. The prescribed dosage, and mode of administration should not be changed. If a participant misses a dose, the missed dose can be given within 1 week. Any changes from the intended regimen must be recorded in the CRF. Infusion start date/time and infusion end date/time should be documented in the patient's CRF.

Drug dispensing/accountability logs will be maintained by a designated unblinded member of the site staff and by the Pharmacy team.

9 PHARMACOVIGILANCE

9.1 Operational definitions for (S)AEs

An Adverse Event (AE) is any untoward medical occurrence in a patient, associated with the use of a medicinal product, whether or not considered related to the medicinal product.

Events meeting the definition of an AE include:

- Exacerbation of a chronic condition (except COPD)
- New conditions detected or diagnosed after trial treatment administration even though it may have been present prior to the start of the trial
- Signs, symptoms, or the clinical sequelae of a suspected interaction
- Signs, symptoms, or the clinical sequelae of a suspected overdose of trial treatment
- Any unfavourable and unintended sign (including an abnormal laboratory finding), symptom, or disease temporally associated with the use of a medicinal product, whether or not considered related to the medicinal product
- Recurrence of an intermittent medical condition (e.g., headache) not present at baseline
- Any deterioration in a laboratory value or other clinical test (e.g., ECG, X ray) that is associated with symptoms or leads to a change in study treatment or concomitant treatment or discontinuation from study drug
- Adverse events that are related to a protocol mandated intervention, including those that occur prior to assignment of study treatment (e.g., screening invasive procedures such as biopsies)

Events that **do not** meet the definition of an AE include:

- Medical or surgical procedure (e.g., endoscopy, appendectomy); the condition that leads to the procedure is an AE
- Situations where an untoward medical occurrence did not occur (social admission to a hospital)
- COPD exacerbation, progression, signs and symptoms (unless they are considered to be related to the trial drug by the investigator; then they would constitute a reaction)

An adverse reaction (AR) is an untoward and unintended response(s) related to the study treatment. All cases judged by either the reporting medically qualified professional or the sponsor as having a reasonable suspected causal relationship to the study treatment qualify as adverse reactions.

A Serious Adverse Event (SAE) or Serious Adverse Reaction (SAR) is defined as any adverse event or adverse reaction in a trial participant that:

- Results in death
- Is life threatening (the subject was at risk of death at the time of event)
- Requires hospitalisation or prolongation of an existing hospitalisation
- Results in persistent or significant disability or incapacity
- Consists of a congenital anomaly or birth defect
- Other serious Important Medical Event an event that may not be immediately life threatening or result in death or hospitalisation but may jeopardise the subject or may require intervention to prevent one of the outcomes listed above should be considered.

A Suspected Unexpected Serious Adverse Reaction (SUSAR) is defined as an adverse reaction that is both unexpected (not consistent with the Reference Safety Information) and also meets the definitions of a Serious Adverse Reaction.

9.2 Safety Assessments

All Adverse events (AEs) will be recorded throughout the study whether serious or not. Members of the research team will ask the participants about AEs at each study time point (see Appendix 1) and will complete the participant AE form, which will be a continuous log so as to capture end dates, and the study serious adverse event (SAE) log. This will be evaluated and classed according to the definitions in sections 9.1.

9.2.1 Reference Safety Information and Expectedness

For the purposes of this trial the Reference Safety Information for determining expectedness of any SAR will be Table 12 (section 6.4.1) of the Investigator's Brochure.

All fatal SAEs will be considered unexpected. No SADRs have been identified for Anti-ST2 as of March 2017 and updated in March 2018. Therefore there are no serious expected Adverse Drug Reactions (ADRs). Any treatment-emergent SAE deemed related to Anti-ST2 treatment during this study will be reported as a SUSAR. There are also a number of expected Serious Adverse Events associated with this disease population, these would be reported as SAEs, but may also be captured as part of the outcome measures exacerbations.

- Administration of MSTT1041A, a protein therapeutic, may lead to the development of anti-MSTT1041A antibodies which could lead to adverse events and/or decreased exposure.
- Hypersensitivity reactions and anaphylaxis have been described with SC administration of mAbs (Corominas et al. 2014). Signs and symptoms may include acute onset (minutes to several hours) of one or more of the following: respiratory compromise, reduced blood

pressure, skin-mucosal involvement, or gastrointestinal symptoms (Sampson et al. 2006). The potential for hypersensitivity to MSTT1041A in humans is unknown. However, as with any large-molecule, therapeutic administration of MSTT1041A may result in systemic reactions.

- Systemic reactions to large-molecule therapeutics can be IgE or non-IgE mediated or due to the release of cytokines and are generally characterized by signs and symptoms such as skin rash, urticaria, pruritus, local or diffuse erythema, angioedema, fever, chills, cough, dyspnea, wheezing, bronchospasm, nausea, vomiting, diaphoresis, chest pain, tachycardia or bradycardia, and/or hypotension, which can be severe or life threatening. Effects typically occur during or within several hours after drug administration, but they may be delayed.
- Injection-site reactions have been described with SC administration of mAbs (Corominas et al. 2014). Signs and symptoms may include pain, itching, erythema, and swelling at the injection site. The reaction may be immediate, although it usually appears within 24-48 hours with variable incidence according to the drug administered.
- Patients with a history of anaphylaxis, hypersensitivities, or drug allergies are excluded from studies with MSTT1041A.
- The intended mechanism of action of MSTT1041A suggests inhibitory effects on immune responses mediated by Th2 cells, leading to the possibility of a decrease in the protective response to infection, particularly helminthic infections (Molofsky et al. 2015). All trial participants will be monitored for signs and symptoms suggestive of infection by collection of vital signs, clinical laboratory tests, and AEs.
- Evidence has shown that the sST2 receptor is a prognostic biomarker of cardiovascular disease outcome (Sabatine et al. 2008; Shah et al. 2009; Weir et al. 2010). Although published findings suggest a possible risk of exacerbation of existing cardiovascular disease in humans, there are no identified cardiovascular risks associated with inhibiting the IL-33/ST2 axis in humans. Patients with active or unstable recent cardiovascular disease are excluded from the trial. Cardiac safety is evaluated with monitoring of vital signs, ECG assessments, the collection of relevant AEs, and other assessments described in the protocol. Lastly, to monitor other factors that may impact upon cardiovascular risk, HbA1c, fasting glucose, and lipid panels are monitored to observe for indication of possible atherogenic and metabolic effects of MSTT1041A exposure. In populations at high risk for pre-existing cardiovascular disease, such as patients with severe COPD, additional monitoring strategies including echocardiography and cardiac biomarkers (e.g., NTproBNP) may also be used.

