#### 1. Safety and tolerability (All visits)

- AE event rate in the 48 weeks of the trial from first dose\*
- SAE event rate in the 48 weeks of the trial from first dose\*

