# 7 Safety and Adverse Events

All safety data will be presented according to the safety population. Any adverse events and serious adverse events occurring from the first dose throughout the trial period will be recorded on the AE CRF, Sponsor's SAE form and SAE tracking log.

An Adverse Event (AE) is any untoward medical occurrence in a patient, associated with the use of a medicinal product, whether or not considered related to the medicinal product.

Events meeting the definition of an AE include:

- Exacerbation of a chronic condition (except COPD)
- New conditions detected or diagnosed after trial treatment administration even though it may have been present prior to the start of the trial
- Signs, symptoms, or the clinical sequelae of a suspected interaction
- Signs, symptoms, or the clinical sequelae of a suspected overdose of trial treatment
- Any unfavourable and unintended sign (including an abnormal laboratory finding), symptom, or disease temporally associated with the use of a medicinal product, whether or not considered related to the medicinal product
- Recurrence of an intermittent medical condition (e.g., headache) not present at baseline
- Any deterioration in a laboratory value or other clinical test (e.g., ECG, X ray) that is associated with symptoms or leads to a change in study treatment or concomitant treatment or discontinuation from study drug
- Adverse events that are related to a protocol mandated intervention, including those that occur prior to assignment of study treatment (e.g., screening invasive procedures such as biopsies)

Events that **do not** meet the definition of an AE include:

- Medical or surgical procedure (e.g., endoscopy, appendectomy); the condition that leads to the procedure is an AE
- Situations where an untoward medical occurrence did not occur (social admission to a hospital)
- COPD exacerbation, progression, signs and symptoms (unless they are considered to be related to the trial drug by the investigator; then they would constitute a reaction)

An adverse reaction (AR) is an untoward and unintended response(s) related to the study treatment. All cases judged by either the reporting medically qualified professional or the sponsor as having a reasonable suspected causal relationship to the study treatment qualify as adverse reactions.

A Serious Adverse Event (SAE) or Serious Adverse Reaction (SAR) is defined as any adverse event or adverse reaction in a trial participant that:

- Results in death

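### The Protocol gives two answers on whether a serious COPD exacerbation is an SAE, and neither document says which one feeds the 48-week SAE event rate

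*Protocol*

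**What the plan says.** **The outcome.** Protocol 3.5.2 and SAP 2.2.1 both list as a secondary outcome the "SAE event rate in the 48 weeks of the trial from first dose".

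**The excluding rule.** Protocol 9.1 lists among events that are not adverse events "COPD exacerbation, progression, signs and symptoms (unless they are considered to be related to the trial drug by the investigator", in which case they count as a reaction. It adds that an SAE "is defined as any adverse event or adverse reaction in a trial participant that" meets a seriousness criterion, one of which is "Requires hospitalisation or prolongation of an existing hospitalisation". SAP section 7 repeats these definitions. On classifying recorded events, Protocol 9.2 says: "This will be evaluated and classed according to the definitions in sections 9.1".

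**The including rule.** Protocol 9.2.1 refers to expected serious adverse events associated with this disease population and says "these would be reported as SAEs, but may also be captured as part of the outcome measures exacerbations". An earlier sentence of the same section deals separately with related events: "Any treatment-emergent SAE deemed related to Anti-ST2 treatment during this study will be reported as a SUSAR". Protocol 9.5 requires all deaths to be reported on the SAE timeline, with no exception for COPD deaths.

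**The planned analysis.** SAP 5.5.1 defers safety analysis to section 7. That section says that adverse events and SAEs "occurring from the first dose throughout the trial period will be recorded". Tables 7 and 8 plan numbers of events, numbers of patients and percentages by arm.

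**The concern.** A hospitalised COPD exacerbation that is not thought drug-related is outside the SAEs under Protocol 9.1 and appears to be inside them under 9.2.1. In a population selected for at least two moderate-to-severe exacerbations in the previous year, this class of event is unlikely to be negligible.

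The choice affects the comparison between arms as well as the totals. If these events are included and the drug prevents exacerbations, the SAE rate favours the drug through efficacy alone. If they are excluded, an excess of COPD admissions on active treatment would not appear in the SAE tables. The primary outcome does not fill that gap, because SAP Tables 5 and 6 do not separate hospitalised exacerbations from those treated in the community.

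**Working it through.** The documents give no SAE rate, no hospitalised share of exacerbations and no rate of other SAEs, so there is no stated figure to reproduce. The check has three parts.

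**1. Can the passages be read together?**
- Under 9.1 an SAE must first be an adverse event or reaction. An unrelated exacerbation is neither, so an unrelated hospitalised exacerbation is not an SAE.
- The 9.2.1 sentence describes events that are reported as SAEs and may also be counted as exacerbations. That overlap requires some serious exacerbations to be SAEs.
- The drug-related exception in 9.1 does not readily supply the overlap, because 9.2.1 covers related SAEs in its own sentence, through SUSAR reporting.
- A COPD death meets the trial's exacerbation definition. It is therefore excluded by 9.1 unless judged related, yet it is on the SAE timeline under 9.5.
- Reporting an event to the sponsor is not the same as counting it in the outcome, which could in principle resolve the conflict. Neither document draws that line.

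**2. How many events are at stake (illustration).** The documents supply 40 patients per arm (80 randomised 1:1), a placebo rate E of 2 or 2.5 per year, and 48 weeks. The hospitalised share h of 10% to 25% is an assumption.

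Events = 40 × E × (48/52) × h
- Low end: 40 × 2 × 48/52 × 0.10 = 7.4
- High end: 40 × 2.5 × 48/52 × 0.25 = 23.1

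So about 7 to 23 placebo-arm events enter or leave the SAE count. This takes full follow-up and no drop-out.

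**3. How far the rate and the comparison could move.** Let s be all other SAEs per patient-year, also an assumption.

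Placebo SAE rate with serious exacerbations ÷ rate without = 1 + h × E / s

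Over a wider assumed grid (h from 5% to 40%, s from 0.1 to 0.5):
- Smallest: 1 + 0.05 × 2 / 0.5 = 1.2
- Intermediate: 1 + 0.10 × 2 / 0.3 = 1.7, and 1 + 0.20 × 2 / 0.2 = 3.0
- Largest: 1 + 0.40 × 2.5 / 0.1 = 11

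A threefold change needs h/s of at least (3 − 1)/E, which is 1.0 at E = 2 and 0.8 at E = 2.5.

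For the comparison between arms, suppose other SAEs are equal and serious exacerbations fall by the design effect (rate ratio RR of 0.5 at E = 2, or 0.6 at E = 2.5). Without serious exacerbations the SAE rate ratio is 1.0. With them it is (s + h × E × RR) / (s + h × E):
- Smallest over the grid: (0.1 + 0.4 × 2 × 0.5) / (0.1 + 0.4 × 2) = 0.5/0.9 = 0.56
- Largest over the grid: (0.5 + 0.05 × 2 × 0.5) / (0.5 + 0.05 × 2) = 0.55/0.60 = 0.92

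**The case against.** **The definitions govern.** Protocol 9.2 sends classification to 9.1, the SAP repeats 9.1, and the amendment history records the exclusion as a deliberate clarification. The 9.2.1 sentence sits in a section on expectedness and does not name COPD exacerbation as an SAE. It could be a loose remark about events that already qualify under 9.1. This narrows the point: the conflict is inside the Protocol, and the SAP follows 9.1. It does not remove it, because 9.2.1 and 9.5 still instruct staff differently and nothing records which instruction shaped the data.

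**The size is unknown.** A reader might infer that the SAE rate changes several-fold. The documents do not support that: the fold-change needs a rate of other SAEs, which they do not give, and the assumed range above starts at 1.2.

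**Harm would still be seen.** A reader might also infer that serious harm would go unnoticed. That goes too far. SAP 5.3 reports deaths and their causes separately, SAP 4.3 gives the DSMC efficacy and safety data by arm, related exacerbations remain reactions, and Table 7 has rows for respiratory tract infections. What stands is that, under the 9.1 rule, no planned table shows COPD hospitalisations by arm.

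**The analysis window is defined.** Recording throughout the trial does not conflict with a 48-week outcome, and the line listing holds start dates. That is correct. The gap is that section 7 and its tables neither apply the window nor compute a rate.

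**Safety is descriptive by design.** Protocol 10.3 says so, and formal tests are not needed here. A descriptive rate by arm is still what the listed outcome calls for.

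**Conclusion.** The point holds as an inconsistency within the Protocol that leaves a secondary outcome undefined. Protocol 9.1 and SAP section 7 exclude unrelated serious COPD exacerbations from SAEs, 9.2.1 implies that they are included, and 9.5 treats COPD deaths as SAEs for reporting. No section says which rule applies to the SAE event rate. The effect on the rate and on the comparison between arms is potentially material but cannot be computed from the documents. The 7 to 23 placebo-arm events rest on an assumed 10% to 25% hospitalised share, and the fold-changes and rate ratios rest on further assumptions about other SAEs.

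Separately, and whichever rule is used, the SAP does not specify the calculation of the outcome it lists: it plans no person-time denominator and no 48-week cut-off.

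**What to change.** 1. Reconcile Protocol 9.1, 9.2.1, 9.5 and SAP section 7, and state which rule was applied to the data. If reporting to the sponsor and counting in the outcome are meant to differ, say so.
2. In SAP section 7, define the SAE rate per person-time from first dose to week 48, by arm, in the safety population. Show it with and without serious COPD exacerbations and COPD deaths.
3. Add a row for COPD hospitalisations by arm, from the primary-outcome data. Add a second row for all-cause hospitalisation, combining these with hospitalisation SAEs and counting once any event present in both sources. The primary-outcome data alone cannot supply this row, because they cover only COPD-related admissions. Deaths by arm are already planned in SAP 5.3.

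The cost is some wording and a few table rows. The SAP revision history shows that version 3.0 follows database lock, so summaries added now should be labelled post hoc.
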